Any participant in Group 3 who has a moderate or severe illness and/or an oral temperature greater than 100.4°F within three days before vaccination 1, or any condition that, in the opinion of the Investigator, would render vaccination unsafe or that would interfere with evaluations may be re-screened and re-randomized with the event which precluded vaccination being added to that participant's medical history. If such an event were to occur within three days of vaccination 2, the vaccination must be delayed but should still occur within the 1-day study window. Participants unable to receive vaccination 2 within the allowed study visit window will remain in the study and be followed for safety.

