7.3.1. Discontinuation of Study Treatment

Study treatment, either administration of antibiotic (ciprofloxacin or doxycycline) or vaccination with AV7909, will be permanently discontinued in any participants if they meet any of the individual participant halting rules described in [Table 4](#). The date when the event occurred or was detected and the specific reason, ie, which criterion was met, for discontinuation of treatment, is to be recorded on the eCRF.

Table 4: Criteria for Discontinuation of Treatment in Individual Participants

No.	Item
1.	
Participants experiencing any of the AEs described in the WARNINGS AND PRECAUTIONS sections of the ciprofloxacin and doxycycline package inserts (provided in the Pharmacy Manual) will be discontinued.
 
In the case of ciprofloxacin, these include, but are not limited to, tendinitis and tendon rupture, hypersensitivity reactions (including rash and jaundice), peripheral neuropathy, central nervous system effects, exacerbation of myasthenia gravis, hepatotoxicity, Clostridium difficile-associated diarrhea, prolongation of the QT interval, and a variety of other serious adverse reactions including severe dermatologic reactions, eg, toxic epidermal necrolysis, Stevens-Johnson syndrome; anemia, including hemolytic and aplastic; thrombocytopenia, including thrombotic thrombocytopenic purpura; leukopenia; agranulocytosis; pancytopenia; and/or other hematologic abnormalities and inflammatory responses, eg, interstitial nephritis; acute renal insufficiency or failure; allergic pneumonitis; hepatitis; jaundice; acute hepatic necrosis or failure.
 
In the case of doxycycline, these include, but are not limited to, Clostridium difficile-associated diarrhea, photosensitivity manifesting as an exaggerated sunburn reaction; super infection and overgrowth of non-susceptible organisms including fungi; severe skin reactions, such as exfoliative dermatitis, erythema multiforme, Stevens-Johnson syndrome, toxic epidermal necrolysis, and drug reaction with eosinophilia and systemic symptoms (DRESS); intracranial hypertension (IH, pseudotumor cerebri) manifesting as headache, blurred vision, diplopia, and vision loss has been observed with papilledema detectable on fundoscopy; delayed skeletal development in the fetuses of pregnant women [tetracyclines/ however, data for doxycycline are limited]. NB: Pregnancy would require discontinuation from the trial (refer to Section 9.4).

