2.	
Grade 2 or greater hypersensitivity, ie, anaphylaxis, allergic reaction (such as, but not limited to difficulty breathing, rapid increase in heart rate, dizziness, nausea, evidence of rash, or periorbital swelling) believed by the PI to be associated with receipt of any of the IPs

AV7909 Anthrax Vaccine

IND 014451

Protocol EBS.AVA.210, Version 3.0 (28 October 2019)

No.	Item
3.	Any Grade 3 or higher systemic reactogenicity symptom assessed by e-diary and confirmed by the PI
4.	Any AE that would pose a risk to the participant as determined by the PI if continued administration of IP were to occur.
5.	Any violation of eligibility criteria discovered after randomization that would pose a risk to the participant, as determined by the PI and agreed to by the Medical Monitor (MM)
6.	Febrile illness (fever > 100.4 °F) within three days prior to either vaccination (Exception: For the second vaccination, the visit may be rescheduled to another day outside this three-day period providing it will not fall outside the required visit window for vaccination two [Section 8.1].)
7.	Receipt of AV7909 associated with loss of cold chain
8.	Suspected or confirmed pregnancy (refer to Section 9.4). (Exception: In the case of suspected pregnancy, if the subsequent serum pregnancy test is negative, the antibiotic dosing may be resumed and the vaccination visit (second vaccination only) may be rescheduled to another day providing it does not fall outside the required visit window for the visit [Refer to Section 8.1].)
9.	Scheduling or other conflict results in the second vaccination visit falling outside the required window
10.	Receipt of prohibited medication (see Section 6.5.1) as determined by the PI and agreed by the MM
11.	Causally-related Grade 3 or higher unsolicited AE as assessed by the PI ^a
12.	Causally-related SAE or potential AESI as assessed by the Sponsor

AE=adverse event; AESI = adverse event of special interest; IP=investigational product; MM = medical monitor; PI=principal investigator, SAE = serious adverse event,

^aAny AE is considered to be related to the vaccine administration if assessed by the PI as being “possibly” or “probably” or “definitely” related.

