All participants who have received at least one vaccination will be encouraged to continue with the scheduled study safety evaluations, including any remaining study visits (safety assessments only), collection of samples for TSH and autoantibodies (only if medically indicated) and the safety follow-up calls. Participants who decline will be encouraged to complete the EWV (see Section 8.1.8) and followed for safety through the 12-Month (Day 388 ± 14d) Safety Follow-up phone call. If the discontinuation was due to an AE, participants will be followed until the event has resolved or stabilized or the participant has been referred to an outside physician.

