AEs ^u , SAEs, AESIs ^v	X	X	X	X		X			X	X	X
Collect TSH & autoantibody samples ^w		X							X		X ^w

For the abbreviations used above please refer to [Table 1](#) of the protocol. *The ± 1 d window applies only to the second vaccination on Day 23 (note: the second course of antibiotic treatment will have to shift accordingly) and needs discussion with CRO. †At Home Days are only those days where both doses of ciprofloxacin are taken at home. § The TBD window only applies to Day 30 and can at best be +1 d but needs discussion with sites and CRO because it will require a 1 day forward shift for all activities thereafter until Day 37 which may not need to shift because of its window. ‡For EWV occurring within the visit window of Day 37, a blood sample for TNA will be drawn.

^aPM and AM admissions must be timed so that ciprofloxacin can be administered in the clinic within a 12 hr ± 30 min window of the prior AM or PM dose.

^b For each PK session, the sites will manage the meals and activity of participants as detailed in [Protocol Section 5.3.1](#) and [Protocol Section 5.3.2](#).

^c Eligibility will be reviewed before each vaccination, either the evening before (ie, on Day 7) or the morning of vaccination (ie, on Day 23).

^d Physical examinations (PE) will be conducted as described in [Protocol Section 8.3.3](#).

^e Electrocardiograms (ECGs) will be conducted and interpreted at screening as described in [Section 8.3.3](#).

^f Vital signs will be administered as described in [Protocol Section 8.3.4](#).

^g Pregnancy tests (serum and/or urine) will be administered to all WOCBP as described in [Protocol Section 8.3.2](#). Serum pregnancy test will be performed at Screening visit for WOCBP, while urine pregnancy tests for WOCBP required before each vaccination will be administered either the evening before (ie, on Day 7) or the morning (ie, on Day 23) of vaccination. Note: for WOCBP in group 1A, UPT is required at Day 3 and Day 7 only (during overnight stay visit); it is not required at Day 30 or 34. FSH test will be performed at Screening visit only for postmenopausal women.

^h Hematology tests will be conducted as described in [Protocol Section 8.3.2](#).

ⁱ Serum chemistry tests will be conducted as described [Protocol Section 8.3.2](#).

^j Urinalyses will be conducted as described in [Protocol Section 8.3.2](#).

^k Urine drug screens will be conducted as described in [Protocol Section 8.3.2](#).

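### Section 6.1.4 and Table 4 item 6 state the rule for fever before vaccination 2 differently: only Table 4 requires the delayed date to clear the three-day fever period, and the events and groups covered do not match.

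*Protocol*

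**What the plan says.** Protocol Section 6.1.4 describes the triggering event in its Group 3 paragraph, for vaccination 1: "moderate or severe illness and/or an oral temperature greater than 100.4°F within three days before vaccination 1", or any condition that the investigator considers unsafe or likely to interfere with evaluations. It then turns to such an event within three days of vaccination 2 and says "the vaccination must be delayed but should still occur within the 1-day study window". The next sentence gives a fallback: "Participants unable to receive vaccination 2 within the allowed study visit window will remain in the study and be followed for safety".

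Protocol Section 7.3.1 says that study treatment "will be permanently discontinued in any participants if they meet any of the individual participant halting rules" in Table 4. Item 6 of that table is "Febrile illness (fever > 100.4 °F) within three days prior to either vaccination". Its one exception is limited to dose 2 and reads: "the visit may be rescheduled to another day outside this three-day period providing it will not fall outside the required visit window".

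The window comes from the schedule of events. The footnote to Table 5 says "The ± 1 d window applies only to the second vaccination on Day 23", which gives Days 22 to 24. The schedules for the other groups carry the same window.

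**The concern.** The two passages share the three-day period and the visit window, but they attach different conditions to the delayed dose. Section 6.1.4 makes the delay mandatory and expects the dose inside the window. Item 6 makes rescheduling optional and requires the new date to clear the fever period. The window leaves at most one day after a Day 23 visit, so that extra requirement often cannot be met. A site that follows the plain words of 6.1.4 could vaccinate a participant who meets a written halting rule.

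The rule also affects the analysis. The PK Population and the Immunogenicity Population both require two AV7909 doses given within the study windows (Protocol Section 10.3; SAP Section 3.2). Whether a recently febrile participant gets the second dose therefore decides whether that participant can be analysed. In Groups 1 and 2 the second antibiotic course has to move with the vaccination date, so sites need to know the rule before the visit.

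**Working it through.** No sample-size or power figure is at issue. The check counts calendar days.

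**Inputs**
- Permitted days for vaccination 2: 22, 23, 24 (Day 23 ± 1 d).
- Trigger: fever within three days before the planned day *p*, so last fever day *f* = *p* − 3, *p* − 2 or *p* − 1.
- Section 6.1.4, read literally: a delayed dose is possible if some day *v* satisfies *p* < *v* ≤ 24.
- Table 4 item 6: a delayed dose is possible if some day *v* satisfies *p* < *v* ≤ 24 and *v* − *f* > 3. This takes a date outside the three-day period to be one more than three days after the fever, and the counts depend on that convention.

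| Planned day | Last fever day | Days from fever to each later permitted day | 6.1.4 (literal) | Item 6 |
|---|---|---|---|---|
| 22 | 19 | 4, 5 | dose possible | dose possible |
| 22 | 20 | 3, 4 | dose possible | dose possible (Day 24 only) |
| 22 | 21 | 2, 3 | dose possible | not possible |
| 23 | 20 | 4 | dose possible | dose possible |
| 23 | 21 | 3 | dose possible | not possible |
| 23 | 22 | 2 | dose possible | not possible |
| 24 | 21, 22 or 23 | no later day | not possible | not possible |

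The outcomes differ on 1 of 3 days for a Day 22 visit, 2 of 3 for Day 23 and 0 of 3 for Day 24. If fever on the planned day itself is counted, the figures are 2 of 4, 3 of 4 and 0 of 4.

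**Alternative reading of 6.1.4.** If its three-day condition applies again to the delayed date, a fever still within three days of Day 24 blocks the dose under both passages, and the outcomes differ on no fever day.

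**Other differences, side by side**
- Events covered: 6.1.4 covers moderate or severe illness, fever and investigator-judged conditions; item 6 covers fever only.
- Groups covered: the Groups 1 and 2 paragraph of 6.1.4 deals with vaccination 1 only. The vaccination 2 sentence comes in the next paragraph, which opens with Group 3. The fallback sentence names no group.

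**Number affected.** The documents give no rate of fever in this period. As an assumption, take 0.5% to 2% of 210 participants: 210 × 0.005 = 1.05 and 210 × 0.02 = 4.2, so about 1 to 4. If all had a Day 23 visit, the three fever days were equally likely and 6.1.4 were read literally, two thirds of these would be handled differently: 1.05 × 2/3 = 0.7 and 4.2 × 2/3 = 2.8, so about 1 to 3 across the trial.

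**The case against.** The strongest reply is that 6.1.4 nowhere permits a dose within three days of a fever. Its condition concerns events within three days of vaccination 2. If the dose moves to Day 24, that condition can be asked again of Day 24, and the fallback sentence then covers anyone who cannot be vaccinated in time. On this view Table 4 spells out what 6.1.4 leaves unsaid. The reading is fair, and it removes the conflict for fever. But it is not written down, and it would leave the instruction to vaccinate within the window workable only for fever on Day 20 when the visit is planned for Day 23. A site could reasonably take either reading.

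A reader might infer three stronger points that the documents do not support.

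- *That most fever cases get the dose under one passage and discontinuation under the other.* The counts above are calendar days, not case frequencies. A majority arises only for a Day 23 visit when fever days before the planned day are counted, and only on the literal reading.
- *That recently ill participants stay in Group 3 but are removed from Groups 1 and 2, biasing the TNA comparison.* Section 7.3.1 applies Table 4 to any participant, so item 6 binds Group 3 as well. The vaccination 2 visit instructions for all five treatment groups include an eligibility review before the dose. The scope of the 6.1.4 sentence is unclear, but nothing exempts Group 3 from Table 4.
- *That Table 4 ignores illness without fever.* Item 6 does, but item 4 covers any adverse event that the investigator judges a risk if dosing continued, and item 9 covers a second vaccination visit that falls outside the window through a scheduling or other conflict. The contrast with discontinuation under item 6 is therefore about fever only.

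The two passages also agree on what follows when the dose cannot be given, as far as follow-up goes. Section 6.1.4 keeps the participant for safety, and Section 7.3.1 says "All participants who have received at least one vaccination will be encouraged to continue with the scheduled study safety evaluations".

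**Conclusion.** The inconsistency is real but narrow. Only item 6 states that the delayed date must clear the fever period, the triggers differ, and the application of the 6.1.4 sentence to Groups 1 and 2 is not explicit. Conflicting outcomes follow only if 6.1.4 is read literally, and then on 2 of 3 preceding fever days for a Day 23 visit, 1 of 3 for Day 22 and none for Day 24.

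The effect on the analysis is likely to be small. About 1 to 3 participants, on an assumed fever rate, compares with planned allowances of 70 − 53 = 17 per group for immunogenicity and 40 − 27 = 13 per antibiotic for PK (Protocol Section 10.2). No effect on the PK or TNA conclusions is shown. The reason to act is that this is a safety rule which sites could apply in different ways, and which also decides entry to two analysis populations.

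**What to change.** Reconcile Section 6.1.4 with Table 4 item 6 so that both state:

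- the same trigger: fever only, or also moderate or severe illness and investigator-judged conditions;
- the same condition on the delayed date within the Day 22-24 window;
- the same consequence when the dose cannot be given in that window;
- that the rule applies to all three groups.

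The sponsor's clinical team decides which version stands; this review proposes none. The cost is a wording change in two protocol passages and a clarification to sites, with no added data or participants.

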6.1.5. Administration of Ciprofloxacin

Ciprofloxacin (500 mg po q 12 hr) will be administered only to participants in Group 1. A total of 31 ± 2 doses will be administered in three courses, the exact format for which will be presented in the Pharmacy Manual.

Group 1A participants will nominally receive 17 of their 31 ciprofloxacin doses in the clinic whereas Group 1B will nominally receive two of their 31 ciprofloxacin doses in the clinic. The

AV7909 Anthrax Vaccine

IND 014451

Protocol EBS.AVA.210, Version 3.0 (28 October 2019)

remaining doses will be taken at home. Doses should be taken at the same times \pm 30 min each day. Doses administered in the clinic will be recorded by the staff with the date and time of administration in each participant's source documents and eCRF. Doses self-administered at home will be recorded by the participant with time of administration in their e-diary. Refer to [Section 8.3.5.1](#) for additional details on the e-diary. If a participant misses a dose, they should be instructed to take the dose as soon as remembered, but no later than within 4 hours of its scheduled time. The participant should then wait until the next scheduled dose. The participant should not take two doses at the same time.

Exact details regarding the format in which the doses will be provided to the participants will be provided in the Pharmacy Manual.

Certain foods and over-the-counter products can interfere with the absorption of ciprofloxacin so prior to administration of doses in the clinic, site staff should ask each participant if they have eaten certain dairy products (such as milk or yogurt) or taken magnesium/aluminum antacids, other highly buffered drugs, or other products containing calcium, iron or zinc since their last dose and if so record this information along with the timing of intake, eg, 6 hours since their last dose. This information along with other precautions that need to be followed when taking ciprofloxacin will be provided to participants when they are given their supplies of ciprofloxacin for self-administration (see [Section 5.3.1](#)).

6.1.6. Administration of Doxycycline

Doxycycline (100 mg po q 12 hr) will be administered only to participants in Group 2. A total of 35 ± 2 doses will be administered in three courses as shown in [Figure 2](#).

Group 2A participants will nominally receive 20 of their 35 doxycycline doses in the clinic whereas Group 2B will nominally receive two of their 35 doxycycline doses in the clinic. The remaining doses will be taken at home. Doses should be taken at the same times \pm 30 min each day. Doses administered in the clinic will be recorded by the staff with the date and time of administration in each participant's source documents and eCRF. Doses self-administered at home will be recorded by the participant with the time of administration in their e-diary. Refer to [Section 8.3.5.1](#) for additional details on the e-diary. If a participant misses a dose, they should be instructed to take the dose as soon as remembered, but no later than 4 hours of its scheduled time. The participant should then wait until the next scheduled dose. The participant should not take two doses at the same time.

Exact details regarding the format in which the doses will be provided to the participants will be provided in the Pharmacy Manual.

Certain foods and over-the-counter products can interfere with the absorption of doxycycline so prior to administration of doses in the clinic, site staff should ask each participant if they have eaten certain dairy products (such as milk or yogurt) or taken magnesium/aluminum antacids, other highly buffered drugs, or other products containing calcium, iron or zinc since their last dose and if so record this information along with the timing of intake (eg, 6 hours since their last dose). This information along with other precautions that need to be followed when taking doxycycline will be provided to participants when they are given their supplies of doxycycline for self-administration (see [Section 5.3.1](#)).

AV7909 Anthrax Vaccine

IND 014451

Protocol EBS.AVA.210, Version 3.0 (28 October 2019)

6.2. Acquisition/Preparation/Handling/Storage/Accountability

6.2.1. Acquisition

AV7909 liquid suspension for injection and oral antibiotics [ciprofloxacin and doxycycline (exact formats will be specified in the Pharmacy Manual)] will be shipped to investigational sites from the drug depot following institutional review board/independent ethics committee (IRB/IEC) and Emergent approval. All shipments will be accompanied by TempTale[®] temperature monitors to record any excursions outside of required storage conditions, ie, refrigerated storage [36 to 46°F (2-8 °C)] for the vaccine and room temperature [68° to 77°F (20-25 °C)] for the antibiotics (ciprofloxacin or doxycycline). Detailed instructions for inventory receipt, temperature excursions, and IP resupply will be provided in the Pharmacy Manual.

6.2.2. Preparation of Investigational Product for Injection

Vaccine vials should be removed from the storage unit and allowed to sit at room temperature for approximately 15 minutes before administration. Vaccine doses should be drawn into a syringe only when administration is eminent. The stability of the vaccine stored in the syringes has not been determined. A site staff member, licensed to administer medication/vaccination, will prepare each dose of AV7909 into a syringe according to the following instructions:

- A separate 1- or 1½-inch 23- or 25-gauge sterile needle and separate 1.0 mL syringe will be used for each participant.
- Gently roll the vial of AV7909 between the hands to ensure that the suspension is homogeneous.
- Visually inspect the product for particulate matter and discoloration prior to preparing into the syringe. If the product appears discolored or has visible particulate matter, DO NOT USE the contents of the vial. THE VIAL SHOULD BE QUARANTINED and reported to the CRO according to the instructions in the Pharmacy Manual.
- Wipe the rubber stopper with an alcohol swab and allow to air dry before inserting the needle.
- Withdraw 0.5 mL of investigational product from the vial into a sterile syringe for administration. The volume and contents of the syringe will be verified by a second person before administration.
- Reseal the vial and cover it with tamper-evident tape to indicate no additional doses may be withdrawn from the vial.

AV7909 should not be mixed with any other product in the syringe.

6.2.3. Handling

Detailed instructions for packaging, labeling, and shipping as well as inventory receipt, and IP resupply will be provided in the Pharmacy Manual.

AV7909 Anthrax Vaccine
IND 014451
Protocol EBS.AVA.210, Version 3.0 (28 October 2019)

6.2.4. Product Storage and Stability

6.2.4.1. AV7909

Each shipment of AV7909 will arrive in a refrigerated carton containing vaccine and a TempTale™ temperature recorder that will be reviewed before use of the vaccine. Immediately upon receipt of each shipment of vaccine, vials are to be refrigerated at 36 to 46°F (2 to 8°C). AV7909 should not be frozen. Storage temperature must be continuously monitored and recorded. To guarantee proper storage conditions, the minimum, actual and maximum temperature in the storage refrigerator shall be continuously monitored for correct temperature. A back-up power source for the refrigerator is required. The study vaccine should be stored in a locked room, with access restricted to necessary site personnel.

